#### STUDY DESIGN

This study uses a pragmatic stepped-wedge cluster randomized trial (SW-CRT) design to evaluate the effectiveness of proactive case detection with a nested qualitative study to assess implementation outcomes of using the CCDT at scale. This study will be conducted in the northern (Bidi Bidi, Rhino, and Omugo settlements) and western (Kyaka II and Kyangwali) settlements in Uganda and is embedded in an ongoing programme until April, 2023.

## Pragmatic stepped wedge cluster randomized design

A visual example of the SW-CRT design with key terminology as recommended by the Consolidated Standards of Reporting Trials (CONSORT) extension can be found in Figure 1. The SW-CRT is described by Hemming and colleagues [15] as a design that:

'...includes an initial period in which no clusters are exposed to the intervention. Subsequently, at regular intervals (the "steps") one cluster (or a group of clusters) is randomised to cross from the control to the intervention under evaluation. This process continues until all clusters have crossed over to be exposed to the intervention. At the end of the study there will be a period when all clusters are exposed. Data collection continues throughout the study, so that each cluster contributes to observations under both control and intervention observation periods. It is a pragmatic study design, giving great potential for robust scientific evaluations that might otherwise not be possible.'

[figure not shown]

Figure 1 Example SW-CRT diagram [16]

In contrast to explanatory trials, in which the CCDT would be evaluated under 'optimal conditions', this study uses a pragmatic approach. The CCDT will be integrated into routine practices and evaluated under these routine conditions, using data that are routinely collected. This implies that; (1) users of the CCDT (i.e. 'community gatekeepers') will be selected from WCH's and TPO's current networks (i.e. community based structures, teachers, community facilitators); (2) community gatekeepers will be trained in using the CCDT during their daily routine activities to detect children and adolescent in need of care and promote help-seeking at TPO; (3) TPO will continue to assess the needs, provide adequate mental healthcare or refer to other organizations as usual to whomever accesses their services; and (4) that data collection follows existing (albeit slightly adjusted) routine monitoring systems.

The staggered approach of a SW-CRT combined with integration in routine practice is chosen because of; (1) the current lack of evaluated low-cost tools to improve community-level identification and help-seeking among children in need of mental healthcare; (2) the promising previous study findings that have shown that the CCDT is an adequate and accurate tool to fill that gap [13, 14]; and (3) logistical reasons that makes the introduction of the CCDT and training of community gatekeepers most practical if it is done per zone and in stages. Additionally, randomisation per zone minimises contamination between the two arms. The SW-CRT design is therefore particularly suitable for this study.

#### **Qualitative study**

In addition to the effectiveness, a nested qualitative study will assess the main outcomes that may influence the implementation at scale. Qualitative feedback from gatekeepers will be obtained during the adaptation process of the CCDT, during supervision meetings and post-implementation.

Since the CCDT will be integrated into routine practices of WCH and TPO, the implementation of the programme and routine data collection continues after the SW-CRT period at least for the entire duration of the programme (i.e., April, 2023).

#### **METHODS**

## **Study Setting**

The CCDT will be introduced in the Bidi Bidi, Rhino, Omugo, Kyaka II and Kyangwali settlements in Uganda. Uganda currently hosts the fourth-largest refugee population in the world with an estimated 1,423,740 refugees and asylum-seekers in the country as of April 2020 [17]. The

majority - 880,367 - are from South Sudan, together with 414,831 from DR Congo, 48,287 from Burundi and 80,255 from other countries [17]. Children represent 61 per cent of the affected population and face a range of ongoing daily stressors such as separation from family members and peers, poverty, discrimination and protection issues that affect their psychosocial wellbeing and mental health, and can increase the vulnerability of developing mental health issues [18]. According to the joint inter-agency Multi-Sector Needs Assessment (MSNA), over 20 per cent of refugee households reported at least one member within the household experiencing psychological distress and requiring support. Furthermore, the settlements in the northern and western part of the country reported high numbers of suicides, with case records reporting up to one case per week [3].

In terms of the administrative structure, each settlement is divided into zones, and zones are divided into villages, clusters and blocks. This is an administrative unit within the settlements where the study will be implemented.

Bidi Bidi, Rhino, Omugo are located in the Northern part of Uganda. Bidi Bidi settlement was established in September 2016, and has rapidly become Uganda's largest, and the world's second largest refugee settlement. Bidi Bidi is composed of five zones, with an estimated total population of children and adolescents aged 5-17 years old of 125,923. Originally established in 1980, Rhino Camp is estimated to be the fourth largest refugee camp in Uganda. Rhino camp is composed of six zones. Omugo is an extension of Rhino Camp and is composed of one Zone, which is sub-divided into six small sub-zones. It has an estimated total population of children and adolescents of 58,898. Kyaka II and Kyangwali are located in Western part of Uganda. Kyaka II was established in 2005, and has a total estimated child and adolescent population of 49,776 and is composed of nine zones. Kyangwali was established in 1960, is composed of ten zones, and has a total estimated child adolescent population of 48,264 [19].

## Selection of study sites

The total number of zones in the study catchment area will be 28 zones. These zones will be selected from Bidi Bidi (3 zones: zone 3, zone 4, zone 5), Rhino (5 zones: Ofua Zone, Odobu Zone, Siripi Zone, Tika Zone, Eden Zone), Omugo (1 zone: Omugo Zone), Kyaka II (9 zones: Sweswe, Byabakora, Mukondo, Itambabiniga, Bwiriza, Kakoni, Buliti, Kaborogota, Bukere) and Kyangwali (10 zones: Maratatu, Mombasa, Maratatu, Kavule, Nyampindu, Kyebitaka, Maratatu, Mukarange, Maratatu, Kentomi) refugee settlements (Annex 2: overview of all the zones names).

The study sites were chosen based on the following criteria:

- 1. Availability of MHPSS services for children, adolescents and caregivers:
  - TPO will be present in each study site. Therefore, each study site has social workers
    and a supervising clinical psychologist with sufficient capacity to respond to an
    increase in children and adolescents seeking help for mental health problems;
- 2. Sufficient and safe referral options for children and adolescents in need of acute (mental) health or child protection assistance not offered by TPO:
  - TPO will be present in each study site and will follow standard operating procedures
    with regards to referral to adequate services in case TPO is not able to respond. This
    will be handled by the supervising clinical psychologists, and includes for example
    referral to psychiatrists at district or regional referral hospitals. Referral pathways for
    each settlement are available upon request.
- 3. Strong community relationships and access to community gatekeepers;
  - TPO and WCH Uganda will be present in all study sites, and the work will be implemented through existing networks of trusted and respected community members.
- 4. Routine data collection systems in place:
  - Sites need to be able to yield reliable outcome data on utilization of TPO's mental healthcare services among children and adolescents or their caregivers.

#### Clusters

The CCDT will be introduced and rolled-out sequentially in 28 geographically distinct zones over the course of 9 months, which are nested within five settlements. The CCDT, and proactive case detection, is implemented at zone-level. The catchment area of a community gatekeeper (i.e., the area they serve) is equal to a zone. Each zone will therefore be considered a cluster in this study. The number of gatekeepers per zone will be dependent on the population size in the zone, our aim is to train 1 gatekeeper per 3000 residents.

Four zones will transition from *pre-CCDT introduction and implementation* (i.e., the control condition) to *CCDT implementation* (i.e., intervention condition), at one-month intervals (i.e., steps), until all zones are implementing the CCDT (Intervention). The order in which the CCDT is introduced in each zone will be determined at random prior to the start of the implementation (before October, 2021). By the end of the SW-CRT period (i.e., 9 months after the start) the CCDT will be introduced and implemented in all 28 zones.

The implementation of the programme and routine detection and utilization data collection continues for the entire duration of the programme (i.e., April, 2023).

# Participant Recruitment and Eligibility Criteria

## Community gatekeepers

A total of up to N=200 community gatekeepers will be selected from WCH's and TPO's existing networks and community-based structures. They include: Village Health Teams (VHTs), teachers, group activity facilitators, child protection committee members, local community leaders and refugee committee leaders. They will be selected, based on the below criteria, by WCH's and TPO's Project Coordinators, responsible for ongoing programming with children and adolescents in each cluster.

## Specific inclusion criteria are:

- At least 18 years of age;
- Trusted and respected members from the community;
- Engaged in promoting child wellbeing;
- Access to children, adolescents and caregivers;
- Demonstrate high level of empathy and interest in children's wellbeing;
- Willing to provide informed consent and participate in supervision meetings to provide feedback on feasibility of the approach;
- Willing to sign and follow WCH's Child Safeguarding Policy, Code of Conduct and Code of Ethical conduct in using the CCDT.

Community gatekeepers will be invited for a two-day training and monthly supervision and debrief meetings (for the duration of CCDT implementation in each of the zones) as part of this project. During the first two months, the supervision sessions will be bi-weekly, after that it will continue on a monthly basis. Consent will be sought for their participation in the project as community gatekeepers and for their participation in the nested qualitative study to capture their feedback on the implementation outcomes (see Annex 4.3). Following usual practices within WCH and TPO's current work, active gatekeepers will be provided transportation and lunch when called for the meeting. They will also be provided airtime to follow up and report on the cases. Regular monthly incentive is not planned under this project. Community gatekeepers from the same zone will be linked to TPO's clinical team serving their zone.

Children, Adolescents, and their Caregivers

Children, adolescents aged 6-18 years old, and their caregivers will be proactively identified by the trained community gatekeepers based on a match with the CCDT (i.e., children and adolescents in need of mental healthcare services). Whenever a trained gatekeeper encounters a child or adolescent that matches with the tool, they will hand out a referral card for TPO and encourage help-seeking at TPO's clinical team serving their zone. Consent procedures are described in the following sections and in Annex 3.

## The program team consists of:

- WCH Uganda's Programme Manager
- TPO's Head of Programmes

- WCH and TPO's M&E Managers
- WCH's Project Coordinators (2) in the West Nile and South West

This team is responsible for the in-country oversight and management of programme activities and will support the contextualization and adaptation of research tools and processes, support data analysis and training of gatekeepers. Furthermore, this team is responsible for routine monitoring and evaluation of the project.

## The clinical team consists of:

- TPO's clinical psychologists
- TPO's social workers
- TPO's volunteer psychosocial assistants

The clinical psychologist leads the clinical team and is overall responsible for assessing the needs and ensuring adequate mental healthcare for the detected children and adolescents – either at TPO or through a referral to external services. The clinical psychologists supervise a team of social workers. Group based focused mental healthcare is provided by social workers, under close supervision from a clinical psychologist. Children and adolescent in need of specialized, individual treatment, will be treated by the clinical psychologist and or referred to external services. Clinical psychologist and social workers are assisted with translations and community mobilization whenever needed by the volunteer psychosocial assistants. The clinical team will be linked to a group of community gatekeepers that are active and live in the same zone.

# **Outcome measures**

#### Primary outcome measure

The primary outcome is utilization of TPO's mental healthcare services among children and adolescents detected by the CCDT. Utilization in this study will be defined as initial encounters with TPO's mental healthcare among children and adolescents 6-18 years old or their caregivers, or re-entry into services for children and adolescents that have not been using TPO's services for 6 months. This is measured in two ways:

(1) Service utilization data: the number of children and or adolescents aged 6-18 years old that seek mental healthcare services from TPO, compared to utilization rates of practice-as-usual (i.e., during the pre-CCDT period). TPO's routinely collected monthly mental health service utilization data will be used for this. Following routine practices, upon intake, TPO's clinical team completes a 'case registration form' (see Annex 4.1).

- (2) The proportion of children and adolescents detected by the CCDT as in need of mental healthcare that seeks help at TPO. Two data sources will be used and compared for this:
  - a. Detection data: number of detected cases per gatekeeper. Gatekeepers will be trained in keeping a log of the number of detected children while using the CCDT (see Annex 4.2). Gatekeeper logbooks will be collected bi-weekly by one of WCH's facilitators attached to the zone and handed over the project officers who will be trained in entering the data in a digital master sheet.
  - b. Service utilization data: Number of cases contacting TPO as a result of a community gatekeeper trained in the CCDT handing out a referral card. The same 'monthly mental health service utilization data' (see outcome 1 above) will be used for this. TPO's clinical team will be trained to ask all new clients (children, adolescents or caregivers) an intake question regarding the reason for seeking help (including the community gatekeeper handing out the referral card as one of the options). This data is entered by the clinical psychologist in the 'case registration form' used upon entry.

The impact of the above outcome measures will be determined in three ways: (1) Trends in monthly utilization data from TPO's service points; (2) comparison of clusters where the CCDT has been implemented (experimental condition) with clusters where the CCDT has not yet been implemented (control condition); and; (3) proportion of CCDT cases detected that sought help at one of TPO's service points. This data will be captured through routine reporting using the referral card, and intake questions.

## Secondary outcome measure

Secondary outcomes include the (1) acceptability and appropriateness of the CCDT according to trained community gatekeepers, (2) the feasibility of using the CCDT at scale, and (3) changes in attitudes towards individuals experiencing mental health problems among community gatekeepers:

1) Acceptability and appropriateness are defined as the satisfaction of community gatekeepers with various aspects of the CCDT tool and perceived fit and relevance of the CCDT tool, adapted to the local context in which it will be employed in the refuge settings. This will be assessed prior to implementation and will be assessed as part of WCH's ongoing program activities. Where, four community adaptation workshops were conducted with 20 community gatekeepers about the different emotional and behavioral problems related to mental health amongst children, these were subsequently used for the creation of the vignettes (one for emotional problems and one for behavioral problems). Furthermore, based on the problems that have been identified in the

communities, we have worked with a local artist to create context-sensitive illustrations. A focus group discussion (FGD) was organized in the 5 settlements in selected zones with 25 community gatekeepers to assess; (a) the level of understanding of the illustrations and vignettes, (b) if they recall a child in their vicinity who experienced similar symptoms, (c) whether they were comfortable by the way the cases were presented in the vignettes and illustrations and (d) the extent to which the CCDT can be successfully used by gatekeepers during their daily routine tasks. The FGD was conducted in their local languages using the translated vignettes including Swahili, Kinyabwisha, Lugbara, Kakwa, Kuku, and Juba Arabic. Based on the FGD further adaptations to the tool were made. Please refer to Annex 4.3 for the topic guides used for this.

- 2) Feasibility is defined as the extent to which the CCDT can be successfully used at scale to detect children and adolescent in need of mental healthcare and promote help-seeking. Qualitative data from gatekeepers will be gathered at two moments:
  - i. During supervision sessions: feedback will be gathered about their satisfaction, the actual fit and utility of the CCDT for everyday use and their motivation with regards to using the CCDT during their daily routine tasks. Questions will focus on the barriers and facilitators that gatekeepers face in using the CCDT. Please refer to Annex 4.3 for the topic guides for supervision.
  - ii. Post-implementation FGDs (n=2) and KIIs (n=6). Questions will focus on the barriers and facilitators that gatekeepers faced in using the CCDT. Please refer to Annex 4.3 for the topic guides for the FGDs and KIIs.

This qualitative data will also be used to interpret the detection trends and supervision attendance per gatekeeper over time, using the gatekeeper logbooks.

3) Attitudes among community gatekeepers towards mental health problems are measured through preferred social distance towards individuals experiencing mental health problems. This will be assessed at pre-training, intermediate and at the end of the project. Social distance is defined as the degree to which people are willing to accept the individuals experiencing mental health conditions in regular social life [20]. Social Distance Scale (SDS) will be used for this. Explicit stigmatizing attitudes questionnaire [21] widely used in mental health [22] in global stigma comparisons [23]; the Nepali version will be adapted for this and has 12 self-report questions on a scale of 1 to 6. Please refer to Annex 4.4. The tool will be translated to the six different languages (Swahili, Kinyabwisha, Lugbara, Kakwa, Kuku, and Juba Arabic), following a process for use in cross-cultural research. Also, we will be conducting cognitive interviews on all measures being

used, in order to assess understandability of the translated tools. The translated tools will be further adapted on the basis of these cognitive interviews.

# Instruments

Table 1 Outcomes, Indicators, Data Source, and Tools

Outcome Measure	Indicator	Data source	Tools/Instruments
Utilization of mental	Initial encounters with	TPO's routine mental	TPO's standardized
healthcare services	TPO's mental	health utilization data.	case registration form
	healthcare per month		(Annex 4.1)
	among children and		
	adolescents 6-18 years		
	old, or re-entry into		
	TPO's mental		
	healthcare services for		
	children and		
	adolescents that have		
	not been using TPO's		
	services for 6 months.		
Proportion of CCDT	Number of CCDT	Detection data:	Gatekeeper Log
positives that sought	positives that utilized	Gatekeeper log on	(Annex 4.2).
help at TPO as a result	TPO's mental	number of detected	
of the CCDT.	healthcare as a result	children.	
	of the CCDT.	Service utilization data:	Single intake question
		TPO's routine mental	included in the case
		health utilization data.	registration form about
			the referral method.
Acceptability and	Satisfaction with	Feedback from potential	Topic guide FGD
appropriateness of the	various aspects of the	gatekeepers prior to	(Annex 4.3)
CCDT	CCDT and perceived fit	using the tool.	
	and relevance of		
	CCDT.		
Feasibility of using the	Barriers and facilitators	Gatekeepers'	Topic guide supervision
CCDT at scale	in using the CCDT in	attendance and	(Annex 4.3)
	routine activities.	feedback during	
		supervision meeting	

		Gatekeepers feedback during post- implementation FGD and KII's.	Topic guide FGD/KII (Annex 4.3)
Attitudes towards mental	Social distance defined	Pre-, intermediate and	Social Distance Scale
health problems	as the degree to which	post-training	(Annex 4.4)
	people are willing to		
	accept the individuals		
	experiencing mental		
	health conditions in		
	regular social life.		

# Sample Size

Sampling takes place at zone level. The number of children and adolescents that will be detected and that will utilize TPO's services/service points per month within each zone will be determined as primary outcome of this evaluation. Using existing utilization data, we estimated the number of zones required to detect a 20% difference in utilization rates pre- to post-CCDT implementation with at least 90% power. Among the zones for which we had existing utilization data available (n=26 zones), we estimated a mean of 17.1 initial encounters with mental healthcare per month per zone (SD=20.1, Median=11.8, IQR=4-24). We conservatively estimated utilization to equal zero in the two zones for which we had missing information. We also conducted a sensitivity analysis by imputing utilization rates for the two zones with missing data by selecting a random number from a Poisson distribution that reflected available utilization data. The intraclass correlation of utilization among zones within a settlement was estimated to be low (ICC=0.115).

Following methods developed by Woertman and colleagues [24], we estimated the minimum sample size required for parallel-groups randomized controlled trial and multiplied that value by the design effect for a stepped-wedge trial over a range of steps to estimate the number of zones required for this study [25]. Twenty-eight zones with seven steps would provide greater than 90% power to estimate a 20% difference in utilization between pre-CCDT and post-CCDT implementation. CCDT will be introduced in four zones per step (i.e., one-month each in length) and monthly utilization data will be collected from each zone the day before the next step.

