# Secondary outcomes:

- 1) Proportion of CCDT positives that sought help at TPO as a result of the CCDT (quantitative)
- 2) Acceptability and appropriateness of the CCDT (qualitative)
- 3) Feasibility of using the CCDT at scale (qualitative)
- 4) Attitudes towards mental health problems (qualitative)

Mixed-effects Poisson regression using a log link with clustering of zones within settlements and repeated measures within zones will be used to estimate the ratio of monthly mental health services utilization from the pre-CCDT to post-CCDT implementation periods. Utilization will be standardized using an offset of the log of the child population size estimate in each zone. CCDT implementation, time, and the interaction between CCDT and time since cross-over will be included as fixed effects. The effect of CCDT will be reported as an incidence rate ratio (IRR, 95% CI). Settlement and zone will be included as a random intercept. Heterogeneity across zones and settlements in time trends and treatment effects will be explored as random effects using the interaction between settlement/zone with time and CCDT implementation. If the assumptions of

Poisson regression are not fulfilled, we will estimate a mixed-effects negative binomial model. All analyses will be conducted using Stata, Version 17.

In addition, descriptive within-group analyses will be conducted to assess the proportion of children and adolescents detected by a gatekeeper using the CCDT that utilized TPO's mental healthcare during the entire project period. Among that group we will also assess the number of children and adolescents that initiated treatment and completed treatment.

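### The printed mean, SD and ICC do not give more than 90% power; the figure needs near-Poisson month-to-month variation within zones, which the protocol does not state

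*Protocol*

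**What the plan says.** The Sample Size section of the protocol sets the aim as being able to "detect a 20% difference in utilization rates pre- to post-CCDT implementation with at least 90% power"; the Population section of the summary repeats this. From 26 zones with data, "we estimated a mean of 17.1 initial encounters with mental healthcare per month per zone (SD=20.1, Median=11.8, IQR=4-24". For the other two zones, "We conservatively estimated utilization to equal zero in the two zones for which we had missing information", with a sensitivity analysis that imputes Poisson values. On correlation it gives one figure: "The intraclass correlation of utilization among zones within a settlement was estimated to be low (ICC=0.115".

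The method is a parallel-group sample size, which the authors "multiplied that value by the design effect for a stepped-wedge trial over a range of steps". The conclusion is that "Twenty-eight zones with seven steps would provide greater than 90% power to estimate a 20% difference in utilization between pre-CCDT and post-CCDT implementation".

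The Clusters section fixes the unit: "Each zone will therefore be considered a cluster in this study". The Randomization section agrees. The analysis text under Secondary outcomes plans a mixed-effects Poisson model with random intercepts for settlement and zone. Its fixed effects are CCDT, time, and an interaction of CCDT with time since cross-over. A negative binomial model is the fallback, and "The effect of CCDT will be reported as an incidence rate ratio (IRR, 95% CI".

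**The concern.** A stepped-wedge design effect needs the correlation of repeated observations within the randomized cluster, here successive monthly counts in one zone. The protocol gives a correlation one level up, among zones of a settlement. It gives no within-zone correlation and no month-to-month variance. It does not say whether 20.1 is the SD of zone averages or of single zone-months, or whether that SD or a Poisson variance entered the formula. The choice decides the answer: 20.1² = 404, against a Poisson variance of 17.1, a ratio of 23.6.

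The power statement is the only justification offered for 28 zones and the 20% target. If ordinary monthly variation leaves power well below 90%, a null result could be read as evidence against a 20% increase when the trial could not reliably show one.

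**Working it through.** **Inputs.** From Sample Size: mean 17.1, SD 20.1, ICC 0.115, 20% difference, 28 zones, seven one-month steps of four zones. Alpha is not stated there; I take 0.05 two-sided, in line with the planned 95% CI, so (1.960 + 1.282)² = 10.507. Seven steps after one control month make 8 periods. A second control month fills the nine months named under Clusters and makes 9.

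**1. The plan's figure from the printed inputs.**
- Difference: 0.20 × 17.1 = 3.42.
- Parallel-group total: 4 × 10.507 × 20.1² / 3.42² = 1,452 zone-months.
- Design effect (k = 7 steps, one count per zone-month, one control month, one measurement per step): [1 + 7ρ] / [1 + 3.5ρ] × 3(1 − ρ) / [2(k − 1/k)]. At ρ = 0.115: 1.805 / 1.4025 × 2.655 / 13.714 = 0.249.
- Zones needed: 1,452 × 0.249 ≈ 362.
- Power with 28: Φ(√(10.507 × 28/362) − 1.960) = Φ(−1.06) ≈ 14.5% (14.7% with 9 periods).

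One-sided 0.05 still needs 295 zones. A mean of 15.88 (17.1 × 26/28, two zones at zero) needs 420. The stated figure is not reproduced.

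**2. What brings it back.**
- Poisson variance, averaged over both conditions: (17.1 + 20.52)/2 = 18.81. N = 4 × 10.507 × 18.81 / 3.42² = 67.6; × 0.249 = 16.8 zones. With 28 zones, power is 98.6%. The same idea with the child as unit needs about 23 zones and gives 94.5%.
- SD 20.1 kept, ICC moved to zone level: 18.5% power at ρ = 0.5, 63% at 0.9, 90% at 0.95 (28.1 zones needed), 94% at 0.958.

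Both routes mean the same thing. At ρ = 0.95 the residual variance is 0.05 × 404 = 20.2, close to the Poisson 18.8.

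**3. How much margin there is.** Information matrix with zone and month effects and no interaction; zone means assumed lognormal (mean 17.1, SD 20.1); count variance μ + CV²μ²; rate ratio 1.20; power = Φ(ln 1.20 / SE − 1.960), with ln 1.20 = 0.1823. I re-ran this and the figures held to within about a percentage point.

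| Assumed within-zone CV | SE of log rate ratio, 8 periods | Power, 8 periods | Power, 9 periods |
|---|---|---|---|
| 0 (Poisson) | 0.0556 | 91% | 93% |
| 10% | 0.0633 | 82% | 85% |
| 20% | 0.0793 | 63% | 67% |
| 30% | 0.0979 | 46% | 49% |

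With two zones at zero and Poisson counts, power is about 88% (8 periods) or 90% (9 periods). With equal zones and a constant dispersion factor, power for 8 / 9 periods is 92% / 94% at 1.0, 91% / 93% at 1.05, 89% / 92% at 1.1, 87% / 89% at 1.2, 79% / 82% at 1.5 and 66% / 70% at 2.

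**4. The planned interaction.** If the target is the effect averaged over exposure time in the model with the CCDT-by-time-since-cross-over term, power with Poisson counts is about 64% (8 periods) or 75% (9 periods).

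**The case against.** The best defence is that the sponsor used a Poisson variance. The text's only named distribution is Poisson (for imputation), the planned model is Poisson, and nothing says that 20.1 was the variance entered. On that reading the claim is met: 94.5% to 98.6% with the printed ICC. Moving the ICC to zone level leaves 92% to 94% with equal zones, so the level error alone does not overturn the figure. This stands, and it means that the decisive gap is the unstated within-zone monthly dispersion.

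Three stronger readings might be inferred, and the documents support none of them.
- That true power is about 14%. This would treat 88.5% of the variance as month-to-month noise, whereas a spread of 4 to 24 across zones is plausibly mostly stable differences between zones.
- That the claim needs exactly Poisson counts and has no margin. Power stays at or above 90% up to a dispersion of about 1.05 with 8 periods and somewhat above 1.1 with 9. Nine periods also hold about 90% with two zones at zero.
- That the planned analysis will inflate type I error. The negative binomial fallback is there to deal with overdispersion.

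It is also fair that the CV range is assumed, that an exposure-averaged effect is not an estimand the protocol names, and that larger effects are well covered. The background reports an almost 50% increase with the adult tool. At a rate ratio of 1.5 and CV 30%, ln 1.5 / 0.0979 = 4.14, or about 99% power. None of this supplies the missing basis for the 20% claim.

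**Conclusion.** The concern holds in a limited form. The stated power does not follow from the mean, SD and ICC printed with it, and the ICC is for a different level from the randomized cluster. The 362 zones and 14.5% only show that the figure cannot be reproduced. More than 90% power is attainable if monthly counts within a zone are close to Poisson, a condition that the protocol neither states nor supports with data. Power then falls quickly: to 82% / 85% at a 10% within-zone CV and 46% / 49% at 30% (8 / 9 periods).

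This rests on two-sided 0.05, lognormal zone sizes, a rate ratio of 1.20 without the interaction, and an illustrative CV range. The actual within-zone variation is not in the document, so the true power cannot be given here.

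**What to change.** Keep the 28 zones. From the existing utilization data for the 26 zones, estimate the month-to-month variance and correlation within a zone. Then re-derive either the power for a 20% increase or the rate ratio detectable with 90% power, by a short simulation under the planned model, saying which effect is targeted once the interaction is included. Replace the power sentence with that result, the variance and zone-level correlation used, and its sensitivity to overdispersion, and bring the summary into line.

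As a guide, without the interaction and with 8 periods, the detectable rate ratio is exp(3.242 × SE): exp(3.242 × 0.0556) = 1.20 with Poisson counts and exp(3.242 × 0.0979) = 1.37 at CV 30%.

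The cost is a short simulation and a few sentences. It depends on the 26-zone data being available month by month. The stated power may become less favourable.
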